The clinical stock of contrast will be used for this study and will be labeled with study specific identifiers tracking the administration and supply. The warmer located in the dual source CT scanner suite will be used to keep the study contrast at required temperature and contrast will not be kept longer than 30 days in the warmer per MUSC policy. The records maintained for the contrast warmer and contrast supply are: temperature, supply of contrast, and contrast bottle used for each patient.

Drugs will be ordered and dispensed from the MUSC inpatient pharmacy per clinical protocol.

Risks from Contrast Media Extravasation

Although extremely rare, it is possible that an IV needle is not properly located within the vein or becomes dislodged when the patient lies down on the examination table. When contrast material is injected, it may then leak into the surrounding tissue. This can be painful and in very few instances has been reported to cause pressure on underlying nerves or vessels that needs to be surgically relieved. Usually, however, a contrast media extravasation is noticed early on by the personnel monitoring the procedure. However, even if a full dose of contrast material is injected in the tissue surrounding a vein, permanent damage is extremely unlikely. Usually the contrast material is fully absorbed by the body within a day without any harmful effect. In addition, in our department we use the latest automated contrast media injector generation, which also comprises of an automated extravasation detection device attached to the arm of the patient. Since the implementation of this device we have not experienced any major extravasation of contrast material.

Beta Blocker (Lopressor)

Common side effects of the drug Metoprolol (a Beta-Blocker) used to slow down the heart rate are: depression, diarrhea, dizziness, itching, rash, shortness of breath, slow heartbeat, and tiredness. Rare side effects are: blurred vision, cold hands and feet, confusion, congestive heart failure (ineffective pumping of the heart leading to an accumulation of fluid in the lungs), constipation, difficult or labored breath.

Nitrate (Nitroglycerine)

Common side effects of the drug Nitroglycerine (a Nitrate available in 0.4 mg or 0.8 mg for sublingual (under the tongue) administration include headache which may be severe and persistent and may occur immediately after use. Vertigo, dizziness, weakness, palpitation (irregular beatings of the heart), and other symptoms of postural hypotension (low blood pressure) may develop occasionally, particularly in upright, motionless subjects. Fainting, which may lead to falls and injuries has also been reported. Flushing, drug rash, and flaky skin have been reported in subjects receiving nitrate therapy.

Use of Regadenoson

The following reactions are listed as warnings and precautions when using regadenoson (Lexiscan™, injected as a 0.4 mg bolus): myocardial ischemia, sinoatrial and atrioventricular nodal block, hypotension, and bronchoconstriction. The following adverse reactions associated with regadenoson are considered transient and are listed in the package insert: dyspnea or urge to breathe deeply, headache, flushing, chest discomfort, angina pectoris or ST segment depression, lightheadedness/dizziness, chest pain, nausea, abdominal discomfort, impaired taste, and feeling hot. Dyspnea can occur during stress myocardial perfusion imaging with associated arrhythmias such as hypoxia induced bundle branch block. The first signs of these rare side effects will cause the termination of the examination.

CT Examination performed with the new Force scanner

The Siemens SOMATOM™ Force is a new computed Tomography X-ray system, which is substantially equivalent to the previous systems (SOMATOM™ Definition and the SOMATOM™ Definition Flash). The SOMATOM™ Force scanner received 510(k) FDA-approval for clinical use on the 17th April 2014.

The SOMATOM™ Force scanner has been used for two other research studies with excellent results. The risks associated with this CT scanner are comparably low to other CT scanners.

Acquisition of patient information

The risks associated with gathering this information are believed to be very low. This information will be stored on a password-protected computer and network server and in a locked office (ART Cardiac Imaging Research Office). The data from this study will be accessible only to the team of researchers from this application.

E.2 ADEQUACY OF PROTECTION AGAINST RISKS

E.2.a Recruitment and Informed Consent

Patients who have been referred for a coronary CTA performed as part of a standard clinical evaluation determined by the treating physician(s) will be eligible for the study and recruited from the MUSC CT schedule. Before the patient comes in for their clinical coronary CTA, their cardiologist or primary physician will be contacted to ensure patient interest in the study and willingness to be approached. Willing patients will be approached and will undergo the informed consent process. Consented subjects will first undergo their clinically indicated coronary CTA; if there is no moderate or significant stenosis on the CTA following an initial interpretation (i.e., normal or near-normal coronary arteries), the patient will not undergo the stress CT perfusion portion of the study and will have their usual care without further testing for cardiac ischemia. However, these patients will be included in the data analysis, belonging to the negative CT population. Patients with moderate, indeterminate, or significant stenosis of any major or large branch epicardial vessel on the CTA will then undergo the stress CT perfusion study. According to current guidelines, it is to be expected that this group of patients will also be clinically referred for further ischemia workup with either SPECT or coronary catheter angiography.

We will also target patients who have undergone SPECT without referral for cardiac CTA; in this case, the coronary CT at rest will be performed as a research procedure with the stress portion following in all cases. The CT perfusion scans will be analyzed and read by two highly trained CT readers (cardiologist and radiologist). In addition to assessing the safety and tolerability of the Lexiscan™ perfusion study, the CT perfusion findings will be compared diagnostically to SPECT and/or invasive catheter angiography if this is performed clinically after the research procedure. These patients must have the clinically indicated SPECT as well as the research cardiac CTA with CT perfusion study completed within 60 days.

Patients who have undergone SPECT with a prior cardiac CTA will also be eligible for this study. These patients will only undergo the stress portion of CT perfusion study. These patients must have the clinically indicated cardiac CTA and SPECT as well as the research CT perfusion study completed within 60 days.

Patients who have undergone MRI perfusion imaging *without* referral for cardiac CTA will also be eligible for this study. For these patients, the coronary CT at rest will be performed as a research

procedure followed by the stress portion of the CT perfusion study. No interpretation will be performed before the stress portion of the exam so all of these patients will receive the stress portion of the exam. These patients must have the clinically indicated MRI stress perfusion imaging as well as the research cardiac CTA with CT perfusion study completed within 60 days.

Patients who have undergone MRI stress perfusion imaging with a prior cardiac CTA will also be eligible for this study. These patients will only undergo the stress portion of CT perfusion study. These patients must have the clinically indicated cardiac CTA and SPECT as well as the research CT perfusion study completed within 60 days.

Only patients with initially negative biomarkers and non-specific-ECG findings will be considered for inclusion in the study in accordance with the Lexiscan package insert. Patients will be screened by approved study personnel from the MUSC SPECT and CT schedules under a HIPAA waiver. Study eligibility determination and study enrollment will be assessed and performed by and investigator in concert with a study coordinator delegated by the PI and approved by the IRB as being authorized to obtain informed consent. The potential use of Lexiscan™ and beta-blockers will be discussed with the responsible physician of record, potential contraindications will be ruled out and permission to approach the patient for possible inclusion will be sought. If the patient is agreeable, they will be approached by one of the licensed physician investigators or designated study coordinators listed on the protocol either prior to or on the day of the CT scan, with a full explanation and request for consent as required by the IRB. MUSC policies regarding patient consent will be followed.

The PI, Sub-I(s) or the SC(s) will obtain informed consent prior to enrollment into the study. The subject will be taken to a quiet/private area (which may include the scanning room, the patient bays or other private areas) and the study purpose, procedures, duration, risks/discomforts, benefits, costs, compensation, alternatives, new information procedures and privacy statements will be explained to the subject.

The subject will be asked to verbally repeat pertinent study information to ensure subject understands the nature of the research. Subjects will be provided the opportunity to ask any questions they may have. Consent will be documented in the currently IRB approved version of the informed consent and will be signed and dated by the person obtaining informed consent and the subject.

E.2.b Protection against Risk

To minimize the risk of post-contrast nephropathy, patients with decreased renal function (creatinine >1.5 mg/dL) will not be eligible for this study. To minimize the risk of allergic reactions to iodinated contrast material, patients with a history of allergic reactions to iodinated contrast material will also be excluded.

Clinical procedures involving Lexiscan™ administration in the Radiology department will be followed: Lexiscan™ administration will be supervised by a licensed cardiologist who will review the patient's medication and medical history for contraindications before the scan, read the patient's pre-scan EKG, be present for Lexiscan™ administration, read the patient's post-scan EKG, and approve the

patient's discharge from the Radiology department. Cardiac resuscitation equipment will be available throughout the scan.

All subjects' medical records will be confined in the usual medical health information office according to their policies and procedures. Each staff member that has approved access to electronic medical records will be given their own password and will be instructed not to reveal that password to anyone else. In addition, those copies of subject information utilized for the research protocol will be kept locked in the Radiology Research suite (ART 2244) in a research specific folder that will identify the subject on the outside of the folder only by initials, subject code (subsequent subject identifiers, i.e. 001, 002, 003, etc., this number will not be able to identify the subject), protocol name, and IRB study number (Pro #). Any data that are used in publication, analyses, etc. will not identify the subject by name, etc. Subjects will be monitored in clinic as per clinical standard practice for any possible side effects and treated as indicated.

E.3 POTENTIAL BENEFITS OF THE PROPOSED RESEARCH TO THE SUBJECTS AND OTHERS

Since the examinations in this study are performed for research purposes and are not used for diagnostic purposes, there are no direct benefits for study participants. However, the knowledge gained from this study may benefit future patients undergoing CT myocardial perfusion imaging. Substantial reductions in radiation dose are expected with the new CT systems. Considering that ionizing radiation is thought to carry a small stochastic risk of inducing cancer, the dose reduction further reduces this theoretical risk. Furthermore, because of the higher attenuation of iodine at low photon energies, the novel CT system can be expected to substantially decrease the amount of contrast material required for CT cardiac perfusion examinations. The small risk of compromising renal function by administration of iodinated contrast material in patients with preexisting renal disease can thus be further minimized.

E.4 IMPORTANCE OF THE KNOWLEDGE TO BE GAINED

Knowledge gained during this study will enable an appreciation of the diagnostic accuracy of Ct cardiac perfusion imaging in comparison SPECT and invasive angiography for diagnosis of acute chest pain and give indications of potential impacts on clinical and diagnostic pathways.

Furthermore, data from this study may potentially allow for substantial reductions in radiation dose and contrast material volume of CT examinations with new CT systems thus further minimizing the small risks of radiation-induced cancer and post-contrast nephropathy. Furthermore, the diagnostic value of CT imaging in detection coronary stenosis may be improved.

E.5 SUBJECT SAFETY AND MINIMIZING RISKS (DATA AND SAFETY MONITORING PLAN)

Eligibility in each case will be confirmed by a named investigator. The source data will be collected by an independent technician and/or study coordinator, maintained securely by the PI and checked by the named investigators. Clinical data will be recorded on a Case Report Form (CRF). However, formal monitoring of site records will not be completed as part of the general conduct of the study. Data collected will be authentic, accurate and complete and the study will be conducted in accordance with the currently approved protocol (and any future approved amendments), Good Clinical Practiced (GCP) and all applicable regulatory requirements.

Any event meeting the criteria of an unanticipated problem involving risks to subjects or others will be reported to the MUSC IRB, as required by HRPP 4.7- Unanticipated Problems and Adverse Events Policy and Procedures. Clinical data will not be monitored by a 3rd party (i.e. Contract Research Organization) or sponsor but the results of the study will be written as a paper and may be submitted as abstracts to various conferences. Every effort will be made to ensure patient safety and confidentiality.

F. FACILITIES AVAILABLE

The Radiology department on the 2nd floor of the Ashley River Tower houses the SOMATOM™ Force on which the myocardial CT perfusion scan will occur. Nursing and physician preparation and monitoring of the patient, including EKG reading and the serum creatinine test, will occur in the patient bays of the Radiology department.

Cardiac catheterization will occur clinically in the Heart and Vascular Center on the 3rd floor of the Ashley River Tower. Clinical SPECT imaging will occur on the 1st floor of the Ashley River Tower. Clinical CTA imaging will occur either in the Radiology department on the 2nd floor of the Ashley River Tower or in the Radiology Department of the MUSC Main Hospital.

G. APPENDIX

The patient satisfaction survey is as follows:

Patient Satisfaction Survey (SPECT/MRI Stress Perfusion)	
How easy or difficult did you find the SPECT or MRI stress perfusion procedure?	
(1) Very Easy
 
(2) Easy
 
(3) Difficult
 
(4) Very Difficult

How do you feel about the length of the SPECT or MRI stress perfusion procedure?	
(1) Very Short
 
(2) Short
 
(3) Long
 
(4) Very Long

How much discomfort did you experience during the SPECT or MRI stress perfusion procedure?	
(1) No Discomfort
 
(2) Some Discomfort
 
(3) Moderate Discomfort
 
(4) A Lot of Discomfort

How nervous were you before and during the SPECT or MRI stress perfusion procedure?	(1) Not Nervous (2) Somewhat Nervous (3) Moderately Nervous (4) Very Nervous
How well do you feel that you understand the SPECT or MRI stress perfusion procedure?	(1) Very Much Understand (2) Moderately Understand (3) Somewhat Understand (4) Don't Understand
How well do you feel that you understand the results of the procedure?	(1) Very Much Understand (2) Moderately Understand (3) Somewhat Understand (4) Don't Understand
How willing would you be to undergo the SPECT or MRI stress perfusion procedure again?	(1) Very Willing (2) Somewhat Willing (3) Somewhat Unwilling (4) Not at All Willing

Patient Satisfaction Survey (CT Perfusion Scan)

How easy or difficult did you find the CT Perfusion Scan procedure?	(1) Very Easy (2) Easy (3) Difficult (4) Very Difficult
How do you feel about the length of the CT Perfusion Scan procedure?	(1) Very Short (2) Short (3) Long (4) Very Long
How much discomfort did you experience during the CT Perfusion Scan procedure?	(1) No Discomfort (2) Some Discomfort (3) Moderate Discomfort (4) A Lot of Discomfort

How nervous were you before and during the CT Perfusion Scan procedure?	
(1) Not Nervous
 
(2) Somewhat Nervous
 
(3) Moderately Nervous
 
(4) Very Nervous

How well do you feel that you understand the CT Perfusion Scan procedure?	
(1) Very Much Understand
 
(2) Moderately Understand
 
(3) Somewhat Understand
 
(4) Don't Understand

How well do you feel that you understand the results of the procedure?	
(1) Very Much Understand
 
(2) Moderately Understand
 
(3) Somewhat Understand
 
(4) Don't Understand

How willing would you be to undergo the CT Perfusion Scan procedure again?	
(1) Very Willing
 
(2) Somewhat Willing
 
(3) Somewhat Unwilling
 
(4) Not at All Willing

H. REFERENCES

4. Cury RC, Budoff M and Taylor AJ. Coronary CT angiography versus standard of care for assessment of chest pain in the emergency department. *J Cardiovasc Comput Tomogr*. 2013;7:79-82.

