Clinical Study Protocol

Use of Lexiscan™ for Myocardial Stress Perfusion Computed Tomography with a 3rd Generation Dual Source CT System

Principal Investigator: [name]

Origination Date: 07/06/2015

Medical University of South Carolina
Department of Radiology and Radiological Science
[name]
[name]

CONFIDENTIALITY STATEMENT

This document is the confidential property of Medical University of South Carolina, Radiology Department. No Part of it may be transmitted, reproduced, published or used by other persons without the permission of the Principal Investigator.

**Use of Lexiscan™ for Myocardial Stress Perfusion Computed
Tomography with a 3rd Generation Dual Source CT System**

Table of Contents

A. SPECIFIC AIMS	3
B. BACKGROUND AND SIGNIFICANCE	3
C. PRELIMINARY STUDIES	3
D. RESEARCH DESIGN AND METHODS (including data analysis)	4
D.1 Research Design	4
D.2 Statistical Methods / Sample Size Justification	10
E. PROTECTION OF HUMAN SUBJECTS	11
E.1 RISK TO THE SUBJECTS	11
E.1.a Human Subject Involvement and Characteristics	11
E.1.b Sources of Materials	14
E.1.c Potential Risks	14
E.2 ADEQUACY OF PROTECTION AGAINST RISKS	17
E.2.a Recruitment and Informed Consent	17
E.2.b Protection against Risk	18
E.3 POTENTIAL BENEFITS OF THE PROPOSED RESEARCH TO THE SUBJECTS AND OTHERS	19
E.4 IMPORTANCE OF THE KNOWLEDGE TO BE GAINED	19
E.5 SUBJECT SAFETY AND MINIMIZING RISKS (Data and Safety Monitoring Plan)	19
F. REFERENCES	22
G. FACILITIES AVAILABLE	22
H. APPENDIX	22

A. SPECIFIC AIMS

Primary Study Aim: The purpose of this study is to evaluate the feasibility, tolerability, safety, and image quality of low-radiation, dynamic perfusion CT of the heart in patients with suspected ischemic chest pain and a moderate or severe stenosis seen on coronary CTA.

The main hypothesis is that CTA with stress and rest perfusion imaging using Lexiscan™ as the coronary vasodilator will be safe, well tolerated, have lower radiation dose, acceptable image quality and be much faster than conventional nuclear perfusion imaging.

Secondary Study Aim: The secondary purpose of this study will be to assess the diagnostic accuracy of CT perfusion imaging compared to either SPECT, MRI stress perfusion, or invasive angiography.

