Patients who have been referred for a coronary CTA performed as part of a standard clinical evaluation determined by the treating physician(s) will be eligible for the study and recruited from the MUSC CT schedule. Before the patient comes in for their clinical coronary CTA, their cardiologist or primary physician will be contacted to ensure patient interest in the study and willingness to be approached. Willing patients will be approached and will undergo the informed consent process. Consented subjects will first undergo their clinically indicated coronary CTA; if there is no moderate or significant stenosis on the CTA following an initial interpretation (i.e., normal or near-normal coronary arteries), the patient will not undergo the stress CT perfusions portion of the study and will have their usual care without further testing for cardiac ischemia. However, these patients will be included in the data analysis, belonging to the negative CT population (see Patient Flow Chart below). Patients with moderate, indeterminate, or significant stenosis of any major or large branch epicardial vessel on the CTA will then undergo the stress CT perfusion study. According to current guidelines, it

is to be expected that this group of patients will also be clinically referred for further ischemia workup with either SPECT or coronary catheter angiography.

Patients who have undergone SPECT *without* referral for cardiac CTA will also be eligible for this study. For these patients, the coronary CT at rest will be performed as a research procedure followed by the stress portion of the CT perfusion study. No interpretation will be performed before the stress portion of the exam so all of these patients will receive the stress portion of the exam. These patients must have the clinically indicated SPECT as well as the research cardiac CTA with CT perfusion study completed within 60 days.

[figure not shown]
Patients who have undergone SPECT with a prior cardiac CTA will also be eligible for this study. These patients will only undergo the stress portion of CT perfusion study. These patients must have the clinically indicated cardiac CTA and SPECT as well as the research CT perfusion study completed within 60 days.

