Patients will undergo dynamic, first pass, stress perfusion imaging during maximal hyperemia induced with Lexiscan™. Imaging will commence approximately 90 seconds after a bolus of Lexiscan™ (0.4 mg per each 5 mL injection). The Lexiscan™ is followed immediately by a bolus of 10 cc saline. In order to achieve the correct timing of the dynamic image acquisition, contrast administration will begin approximately 80 seconds after the Lexiscan™ bolus to allow the contrast to reach the heart at the moment of maximal hyperemia. Data will be acquired for 30 seconds with both X-ray tubes set at 80 – 100 kV, a gantry rotation time of 0.28 seconds, and a tube current of 300 mAs per rotation. Temporal resolution is approximately 75 ms. Patients will be instructed to hold their breath for the first 15 seconds of the scan, as this is the most important portion of the data acquisition for quantifying myocardial blood flow. They will then be instructed to breath shallowly for the remaining 15 seconds. Perfusion imaging is performed in an ECG-triggered shuttle mode in which the table shifts between two z-positions of the heart to allow coverage of nearly the entire left ventricle. End systolic imaging is used to reduce motion artifacts, to image the heart at its smallest dimensions, and to reduce beam-hardening artifacts from contrast in the LV cavity. The relatively fast rotation time combined with the dual source system gives markedly improved temporal resolution, which helps to reduce motion artifacts associated with the rise in heart rate that frequently occurs after Lexiscan™ administration. With a detector width of 38 mm and 10% overlap between the two imaging positions, the coverage of the acquisition is 73 mm. In some patients, small portions of the base or apex could be cut off. A total of 14 or 15 image volumes during myocardial passage of the contrast bolus will be acquired. CT MPI studies will use 40 – 50 mL of contrast agent (Ultravist 370) administered at a flow rate of 4 – 6 mL/s. Following the perfusion imaging, the Lexiscan™ will be

reversed with 1 mg/kg of aminophylline per standard clinical protocol if indicated by the supervising physician.

CT Perfusion Data Reconstruction and Analysis:

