This study is intended to primarily demonstrate feasibility, safety, and tolerability of Lexiscan™ for use as a coronary vasodilator during perfusion CT imaging. The study is not powered to prove the diagnostic accuracy of perfusion CT imaging with low radiation compared to SPECT or the current gold standard approach of invasive coronary angiography with invasive fractional flow reserve (FFR) measurement. Nonetheless, we will use the available comparative data for each technique (SPECT, MRI stress perfusion imaging, and invasive angiography) to help design subsequent clinical trials that are adequately powered for an accuracy endpoint. We anticipate that about 15 out of the 30 participants who undergo the CT perfusion portion of the study will have available cath comparisons.

Continuous data are displayed as mean ± SD, if normally distributed, or median and interquartile range if not normally distributed. Binary data are are displayed as proportions. Data will be reported as means ± SD or rates with 95 percent confidence intervals. A difference with P value of 0.05 or less will be considered significant.

Subjective image quality scores will be compared using the Chi-squared test with the Yates continuity correction for categorical variables and inter-observer agreement for image quality will be calculated using Cohen kappa (K) statistics and interpreted as follows: ≤ 0.20 slight or poor agreement, 0.20 – 0.40 fair agreement, 0.40 – 0.80 moderate agreement, ≥ 0.80 excellent agreement. For each group, comparisons of patient characteristics will be performed using the Chi-squared test for categorical variables and t-test or Mann-Whitney-U-test for continuous variables as appropriate.

Quantitative data (CNR, radiation dose) will be tested using a non-parametric significance test.

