Patients with heart rates >65 bpm may receive beta-blockers in order to lower the heart rate to values <60 bpm. Patients with contraindications to the use of beta-blockers (chronic obstructive pulmonary disease, asthma sensitive to beta agonists, second- or third-degree heart block, hypotension (<100 mm Hg systolic) are in principle eligible for participation in the study – however, no beta-blockers will be used in such individuals.

There will not be any eligibility criteria for any subpopulations. In addition, there will not be any targeted involvement of special classes of subjects, such as fetuses, neonates, pregnant women, children, prisoners, institutionalized individuals, or others who may be considered vulnerable populations. All race and ethnicities and both genders will be considered for inclusion into the study. Subjects under the age of 18 will not be considered for inclusion into this study. This research will only be conducted at the Medical University of South Carolina.

Targeted/Planned Enrollment Table

Total Planned Enrollment: 100

TARGETED/PLANNED ENROLLMENT: Number of Subjects			
Ethnic Category	Sex/Gender		
	Females	Males	Total
Hispanic or Latino	0	0	0
Not Hispanic or Latino	50	50	100
Ethnic Category: Total of All Subjects*	100		
Racial Categories			
American Indian/Alaska Native	0	0	0
Asian	0	0	0
Native Hawaiian or Other Pacific Islander	0	0	0
Black or African American	17	17	34
White	33	33	66
Racial Categories: Total of All Subjects*	50	50	100

E.1.b Sources of Materials

The research materials that will be obtained from living human subjects are: the cardiac SPECT, MRI stress perfusion, coronary catheterization, CT, and all applicable other imaging studies (e.g. echocardiography), progress notes, medication records, vital signs, medical history and demographics, and all other applicable clinical information.

The Principal Investigator, Sub-Investigator(s) and the Study Coordinator(s) will be the only personnel who will have access to subject identities, with the exception of any regulatory personnel (MUSC IRB auditors, etc.). All subject identities will be removed prior to publication.

E.1.c Potential Risks

Patient discomfort

The study prolongs the discomfort for the patient of lying supine by approximately 30 minutes for the CT study. Subjects may find it uncomfortable to lie still during the scans. A study duration of no more than 60 minutes room time will be used to minimize this discomfort.

Vein puncture

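### The speed claim in the main hypothesis has no objective time measure or analysis, and the MRI exclusion as worded also removes usable CT doses from the new-versus-older scanner comparison

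*Combined protocol and SAP*

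**What the plan says.** **Speed.** The hypothesis in Section A (Specific Aims) holds that CTA with stress and rest perfusion imaging will, besides being safe and well tolerated, "have lower radiation dose, acceptable image quality and be much faster than conventional nuclear perfusion imaging". The Primary Study Aim just above it does not mention speed: "The purpose of this study is to evaluate the feasibility, tolerability, safety, and image quality of low-radiation, dynamic perfusion CT of the heart". Nor does the opening of D.2: "This study is intended to primarily demonstrate feasibility, safety, and tolerability".

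Time appears in three kinds of place:

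- D.1, CT myocardial perfusion protocols, for the stress acquisition: "Data will be acquired for 30 seconds with both X-ray tubes".
- E.1.c, Potential Risks: "The study prolongs the discomfort for the patient of lying supine by approximately 30 minutes for the CT study", followed by "A study duration of no more than 60 minutes room time will be used to minimize this discomfort".
- The satisfaction survey (D.1 and the Appendix), which asks for an opinion of the length of the test on a four-level scale from very short to very long. There is one form for CT and one combined form for SPECT or MRI.

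**Dose.** D.1, Analysis of radiation dose, records CT dose for every acquisition and computes a combined rest-plus-stress SPECT dose. It states one comparison: CT perfusion dose on the new scanner against the institution's previous scanner. It then excludes patients whose comparator was MRI from the radiation dose analysis, without limiting that exclusion to any one comparison.

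**The concern.** A main hypothesis should map onto something measured and analysed. Here one of its elements, speed relative to nuclear imaging, has no variable behind it. The report would either be silent on the claim or support it with a time definition chosen after the data are in hand.

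The dose wording raises a different problem. A patient who had MRI has no SPECT dose, so leaving that patient out of a CT-versus-SPECT dose comparison is sensible. The new-versus-older scanner comparison uses only CT dose, which that patient does have. Applied literally, the rule discards usable data from the only dose comparison the section spells out, with nothing gained.

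**Working it through.** The plan gives no sample size, effect size or precision for time or dose, so it has no figure of its own to reproduce on this point. The check is mainly a reading of the text.

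**Step 1: what is measured.** D.1 defines image quality scores, SNR and CNR, radiation dose, a safety checklist, 30-day events and the satisfaction survey. It defines no acquisition time, room time or time to result, for either modality. No SPECT duration appears anywhere in the document.

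**Step 2: what is analysed.** D.2 names CNR and radiation dose for quantitative testing. Its general rules (mean and SD, 95% confidence intervals) would serve any continuous variable, but no time variable is defined for them to act on. D.2 assigns no analysis to the survey.

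**Step 3: could an existing time figure stand in?** The three CT figures describe different things:

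| Figure | What it describes | Where |
|---|---|---|
| 30 seconds | stress acquisition only | D.1 |
| about 30 minutes | added time lying supine | E.1.c |
| 60 minutes | upper limit on room time | E.1.c |

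None is an outcome and none has a SPECT counterpart. The sessions also differ by route. Of patients with a prior CTA, D.1 says: "These patients will only undergo the stress portion of CT perfusion study". Their research session therefore omits the CTA, while the hypothesis concerns CTA together with perfusion imaging.

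**Step 4: which dose comparisons need which data.**

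| Comparison | Data needed from the patient | Available on the MRI route? | Stated in D.1? |
|---|---|---|---|
| New versus older CT scanner | CT dose | yes | yes |
| CT versus SPECT | CT dose and SPECT dose | no, if there was no SPECT | implied by the SPECT dose calculation, not stated |

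The exclusion fits the second row but is written so that it also covers the first.

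**Step 5: size of the dose loss.** D.2 works with 30 patients having CT perfusion; its 510 regions follow from 30 × 17 = 510. The MRI share f is not given. The number of CT doses lost is 30 × f:

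- f = 0%: 0 lost, 30 kept
- f = 10%: 3 lost, 27 kept
- f = 20%: 6 lost, 24 kept

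These shares are assumptions. The lower end is plausible because E.1.a describes screening from the SPECT and CT schedules and names no MRI schedule.

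**The case against.** **Speed is peripheral.** It occurs in the hypothesis sentence but not in the Primary Aim or in D.2's statement of intent, and no sample size rests on it. This stands, and it is why the point is minor. It does not make the claim testable.

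**The survey does address length.** This stands in part. The item is asked for both CT and SPECT/MRI, so it would be wrong to infer that the plan collects nothing on time. What it collects is an ordinal opinion, on a form that combines SPECT and MRI, with no analysis named. That cannot show that CT takes less time.

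**The choice of clock could decide the answer.** A reader might set the 30-second acquisition against the 60-minute room limit and infer that the result swings enormously with the definition. The documents do not support that. The figures are unlike quantities, the 30 seconds covers only one part of the examination in the hypothesis, and with no SPECT duration given nobody can show that any choice would reverse the conclusion. All that follows is that the clock should be fixed in advance.

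**The MRI exclusion was probably meant only for CT versus SPECT.** That may well be so. The text does not say it, and one phrase would settle it.

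**The timestamps may not be available.** E.1.b lists as research materials "the cardiac SPECT, MRI stress perfusion, coronary catheterization, CT, and all applicable other imaging studies". That covers the studies themselves; access to acquisition times is an inference, so the fix has to allow for gaps.

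**Conclusion.** Both parts hold, and both are minor.

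1. The plan has no objective time measure for CT or SPECT and no time analysis, so it cannot support or refute the speed element of its own hypothesis. This rests on the text alone. Safety, tolerability, feasibility and image quality are unaffected.
2. Read literally, the MRI exclusion removes CT doses that the new-versus-older scanner comparison could use. The loss is 0 to 6 of 30 doses for an assumed MRI share of 0 to 20%, and may be near zero. A reader might infer a material loss of power or a biased scanner comparison. The documents do not support either: the MRI share and the size of the older-scanner group are not given, and D.2 assigns dose an unnamed non-parametric test.

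The more consequential gap in the dose section is that the hypothesis claims lower dose than nuclear imaging, while no sentence there says that CT dose will be compared with SPECT dose.

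**What to change.** **Time: measure it or drop it.**

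- Record start and stop times for each component: rest CT/CTA, stress CT, rest SPECT and stress SPECT. That is up to 4 × 2 = 8 fields per patient.
- Where a scan preceded enrolment, use image timestamps if they can be obtained.
- Use the same clock on both sides of each pair, and add sessions together when parts of an examination were done separately, as with a prior CTA.
- Report the within-patient CT-minus-SPECT difference with a 95% confidence interval, in patients who had both tests. On the plan's own expectation this is at most 30, and probably fewer: MRI-route patients may have no SPECT, and D.1 expects patients with stenosis to go on to either SPECT or catheter angiography.
- Otherwise delete *much faster* from the hypothesis.

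**Dose: three changes of wording.**

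- Limit the MRI exclusion to the CT-versus-SPECT comparison.
- State that comparison explicitly as paired: total CT dose (CTA plus stress) against total SPECT dose (rest plus stress).
- Keep CT doses from MRI-route patients in the new-versus-older scanner comparison.

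**Cost.** Up to about eight data fields, some filled retrospectively, and a few sentences. No extra scans or visits are needed. The drawback is that timestamps give acquisition span and omit preparation and recovery. Where they are the only source, the SPECT and CT times must both be expressed as acquisition span, and the report must say so.
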